## **10.0 EVALUATION DURING TREATMENT/INTERVENTION**

Immediately after the first request for the analgesia, before administration of the open label morphine 2 mg IV, every 10 minutes thereafter and at the time of the second request for the analgesia, we will record (See Appendix 4):

**Memorial Sloan-Kettering Cancer Center  
IRB Protocol**

**IRB#: 05-025A(7)**

- Pain relief scores on a 0-100% scale
- Pain intensity scores on a 0-10, 11 point, verbal scale
- Respiratory rate
- Side effects from the pain medication and their severity rated by the patient on a 0-3 scale (none, mild, moderate, severe)
- Time to the second request for the pain medication
- Global assessment. The patients will be asked: "How effective was the medication in relieving your pain?" The patient will choose among: 1) not effective 2) slightly effective 3) moderately effective 4) very effective 5) extremely effective.

Immediately before administration of the study drug, i.e. morphine 2 mg IV or morphine 1 mg with methadone 1 mg IV, every 10 minutes and at the time of the third request for analgesia, we will record (See Appendix 5):

- Pain relief scores on a 0-100% scale
- Pain intensity scores on a 0-10, 11 point, verbal scale
- Respiratory rate
- Side effects from the pain medication and their severity rated by the patient on a 0-3 scale (none, mild, moderate, severe)
- Global assessment. The patients will be asked: "How effective was the medication in relieving your pain?" The patient will choose among: 1) not effective 2) slightly effective 3) moderately effective 4) very effective 5) extremely effective.
- Time to the third request for the pain medication (upon which the study is completed)

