## 5.0 THERAPEUTIC/DIAGNOSTIC AGENTS

Morphine, a phenanthrene derivative, is the prototype opioid agonist. All other opiates are compared to morphine in determining their relative analgesic potency. Because of its widespread availability, it is the drug of choice for the treatment of post-operative pain and severe pain associated with cancer (17). There is no ceiling to its analgesic effect, although side effects, particularly sedation, respiratory depression and confusion may intervene before optimal analgesia is achieved (18, 19). It is metabolized in the liver, where it undergoes glucuronidation at the 3 and 6 positions. In single dose studies it is equipotent to methadone (20). The duration of analgesia is 3-4 hours. Because of the low dose used, we do not expect

**Memorial Sloan-Kettering Cancer Center  
IRB Protocol**

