**IRB#: 05-025A(7)**

significant side effects in patients who have been already receiving morphine for over 12 hours.

Methadone, the 50/50 racemic combination of d-methadone and l-methadone, has been in widespread use for decades and has been studied extensively. There is no evidence of organ toxicity from chronic opioid use, including chronic methadone use (21). The main concern when using methadone for the treatment of pain is its long and unpredictable half-life which, with chronic administration, is associated with the risk of delayed opioid toxicity with side effects such as sedation, confusion and respiratory depression. For this reason methadone is generally viewed as a second line opioid, generally used after other opioids with a more predictable dose-response have been tried. This is a single dose study and therefore drug accumulation will not occur. Because of the low dose used, we do not expect toxic effects or significant side effects in patients who would be receiving morphine for over 12 hours by the time the study begins.

Preservative-free methadone and morphine combination (1 mg morphine+1 mg methadone) and parenteral morphine (2 mg of morphine IV) will be prepared, vialled and blinded by the MSKCC pharmacy. The methadone injection will be provided in single use vials containing 1 mg/ml, 0.5 ml, or 1 mg/ml, 2 ml. The morphine injection will be provided in vials containing 5 mg/ml, 1ml. Morphine and methadone are compatible for 7 days. Drugs will be dispensed by the pharmacy to the clinical investigator in a blinded fashion on the day of the study.

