**IRB#: 05-025A(7)**

continuous infusion and 1mg every 10 minutes as needed and titrated up as needed. CABs as needed will be available (See Appendix 1).

The day after the surgery the PCA will be stopped for the period of the study. We will ask the patient to request pain medication as soon as he feels moderate pain. The doctor will be present to monitor the time of the patient's request, assess pain intensity and administer drugs to replace the PCA promptly upon the patient's request. If two hours pass before a first request for pain medication is made, the patient will be removed from the protocol. Not more than two patients per doctor per floor will be enrolled on the same day. During the period of the trial, the doctor will have no clinical or other responsibilities.

1. When the patient requests pain medication, baseline pain intensity will be assessed and open label 2 mg of morphine IV administered. After administration of morphine, the patient's pain relief, pain intensity, respiratory rate, and side effects reported by the patient will be assessed every 10 minutes, and at the time of the second request for analgesia medication. If four hours pass before a second request for pain medication is made, the patient will be removed from the protocol.

2. Immediately upon a second request for analgesia, the study drug in a double blind fashion (1 mg of methadone IV plus 1 mg of morphine IV or 2 mg of morphine IV), will be administered by the doctor. After administration of the study drug, the patient's pain relief, pain intensity, respiratory rate, and side effects reported by the patient will be assessed every 10 minutes, and at the time of the third request for analgesia medication.

3. Upon a third request for analgesia medication or after four hours if no medication is requested, the study is completed and the PCA will be restarted at the pre-study dose. If four hours pass before a third request for pain medication is made, the patient will be removed from the protocol.

The total amount of opioid available to patients will be equivalent to the standard amounts used after retroperitoneal lymph node dissection.

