## **11.0 TOXICITIES/SIDE EFFECTS**

Methadone has been in widespread use for decades and has been studied extensively. The most frequently observed side effects include sedation, nausea, vomiting, constipation, confusion and hallucinations, which are more pronounced in ambulatory patients and less common at lower doses. Methadone accumulation is not a concern in the current study because of the single dose design. Methadone-related side effects are easily reversed by naloxone.

Morphine is the standard opioid used for post-operative care. Subjects will receive a dose of 2 mg morphine intravenously, immediately when they request the analgesia medication. This dose may be slightly lower or higher than the dose of morphine received via continuous infusion previously. This may result in temporary improvement or worsening of pain control. The most serious side effect is respiratory depression, particularly with rapid administration. Low doses of intravenous morphine have little effect on cardio-vascular stability. High dose morphine may cause sympathetic over activity, dysphoria and convulsions. Nausea, vomiting, constipation, headache, anxiety, pruritus and urinary retention may be seen at lower doses and easily reversed by naloxone.

Given the relatively small amount of opioid used in the study drug (morphine 1 mg plus methadone 1 mg), we do not expect any side effects. However, due to the potential for synergism and, therefore, potentiation of the effect, we will closely monitor the patient for the presence of side effects (see Section 10, Evaluation During Treatment). NCI Common Toxicity Criteria 3.0 will be used to categorize and grade toxicity. Toxicities of grade 2 or less will be treated symptomatically. For patients with grade 3 or 4 toxicities, morphine and methadone will be stopped and an appropriate alternative analgesic regimen will be started.

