### 14.0 BIostatISTICS

The primary comparison will be the difference in pain relief recorded as the "area under the curve" (AUC) between the initial 2 mg morphine dose and the study drug. AUC will be estimated by plotting % of pain relief over the time (see Appendix 6).

Time (t) for each AUC will include:

For area A:

- t0, time of the first request for the analgesia and opened administration of 2 mg morphine;
- t2, 3, ..., time of assessments 10 minutes apart
- tn, time of the second request for analgesic medication and study drug administration.

For area B:

- t0 time of the second request for analgesic medication and study drug administration;
- t2, 3, ..., time of assessments 10 minutes apart;
- tn, time of the third request for analgesic medication and completion of the study.

Pain relief at the time of the request for pain medication will be considered baseline and each patient will serve as his own control. Should the pain relief score at the time of the second pain medication administration be reported higher than the baseline, projected AUC will be used, extending it to the baseline.

AUC for 2 mg morphine (area B1) and AUC for a combination of 1 mg morphine and 1 mg methadone (area B2) will be compared to the AUC for open label 2 mg morphine (area A).

**Memorial Sloan-Kettering Cancer Center  
IRB Protocol**

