**IRB#: 05-025A(7)**

**SYNERGY: Appendix 3: Pre-treatment Evaluation**

Patient name:  
MRN:

Age	
Ethnicity	
Weight	
Height	
Past Medical History	
Past Surgical History	
H/o Opioid Use	
Current Medications	
Drug-related side effects using NCI scale (sleepiness, confusion, hallucinations, nausea/vomiting, others), 0-3, 4-point scale	

Memorial Sloan-Kettering Cancer Center  
IRB Protocol

IRB#: 05-025A(7)

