**Follow-up 10 minutes after treatment started**

- On a scale of 0-100%, where 0 is no pain relief and 100% is complete pain relief, how would you rate your pain relief right now?
- On a scale of 0-10, where 0 is no pain and 10 is the worse pain you can imagine, how would you rate the intensity of your pain right now?
- Respirations per minute: \_\_\_\_\_
- Side effects reported by the patient: \_\_\_\_\_

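### After dosing, sedation and confusion are recorded only by patient report, so they may be under-recorded, and a sedation-related delay in requesting analgesia can distort the B/A ratio

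*Combined protocol and SAP*

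**What the plan says.** **Risks named.** Section 5.0 says of morphine that "side effects, particularly sedation, respiratory depression and confusion may intervene before optimal analgesia is achieved". Section 11.0 puts sedation first among the common side effects of methadone and also lists confusion. It expects no side effects at the study dose, but because synergism could potentiate the effect it promises close monitoring and refers to Section 10.0 for how.

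**How they are recorded.** Section 10.0 lists respiratory rate and "Side effects from the pain medication and their severity rated by the patient on a 0-3 scale (none, mild, moderate, severe". Section 9.0 says that "respiratory rate, and side effects reported by the patient will be assessed every 10 minutes, and at the time of the third request", and Section 4.2 agrees. At each 10-minute check, Forms 1 and 2 (Appendices 4 and 5) give one blank line, "Side effects reported by the patient", with no named symptom and no severity field. Only the pre-treatment form (Appendix 3) names the symptoms: "Drug-related side effects using NCI scale (sleepiness, confusion, hallucinations, nausea/vomiting, others), 0-3, 4-point scale".

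**Other safety provisions.** A doctor without other duties is present (Section 9.0). Toxicity is graded by NCI criteria, with action at grade 3 or 4 (Sections 11.0 and 17.0). Neither the grader nor the source of the grade is stated.

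**Primary outcome.** Sections 12.0 and 14.0 define an AUC of patient-scored relief. Area B ends at the "time of the third request for analgesic medication and completion of the study". If four hours pass without a third request, Sections 4.2 and 13.0 remove the patient; item 3 of Section 9.0 says both that the study is then complete and that the patient is removed.

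**The concern.** Two consequences follow from relying on the patient for this information.

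The first is safety capture. A drowsy or confused patient is poorly placed to report drowsiness or confusion. The plan's answer to possible potentiation is the monitoring in Section 10.0, yet that section gives the doctor at the bedside nowhere to record what is seen, apart from respiratory rate. The sleepiness and confusion items at baseline have no counterpart after dosing.

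The second is the primary endpoint. The same patient may be slower to ask for medication, and the request is what closes the area. If the combination sedates more than morphine alone, part of a larger area B2 could reflect late requests rather than better analgesia. Dividing by area A does not remove this, because area A follows open-label morphine in both arms. Randomisation does not remove it either, because the sedation would itself be a drug effect. Sedation equally common in both arms would not bias the comparison of arms.

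**Working it through.** **1. The plan's own figure.** Section 14.0 gives 35 completers per arm, a difference of 0.68 within-group SD in mean B/A, and a two-sided t-test at 0.05. The noncentrality is 0.68 × √(35/2) = 2.84 on 68 df, giving power of 80.1%. The stated 80% is reproduced and is not in question.

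**2. One patient's ratio (assumed values).** The documents give no relief profile. Take relief at the request as 0% and leave out Section 14.0's projection rule. The area added by a delay of d minutes at recorded relief r is d × r.

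- Assumed area without delay: 60 min × 40% = 2,400 %-min.
- Relief recorded as 30% during the delay: 15 min adds 450 (18.8%), 30 min adds 900 (37.5%), 60 min adds 1,800 (75%).
- A 60-minute delay at other recorded levels: 0% adds 0; 10% adds 600 (25%); 20% adds 1,200 (50%).

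As a cross-check, use a curve of 0, 40, 50, 40, 30, 20, 10% at 0 to 60 minutes. By the trapezoid rule the area is 10 × (0/2 + 40 + 50 + 40 + 30 + 20 + 10/2) = 1,850 %-min. With that curve in both periods and a 60-minute delay in B only:

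| Relief recorded during delay | B/A |
|---|---|
| 0% | 1.00 |
| 10% | (1,850 + 600)/1,850 = 1.32 |
| 20% | (1,850 + 1,200)/1,850 = 1.65 |
| 30% | (1,850 + 1,800)/1,850 = 1.97 |

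Delay alone does nothing. The ratio rises only if a relief score above zero is recorded or carried through the delay.

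**3. The comparison of arms (assumed values).** Suppose a share f of the combination arm has B/A raised by s SD for this reason alone, with no true effect and the SD unchanged. The mean shift is δ = f × s. By the normal approximation the two-sided rejection probability is 1 − Φ(1.96 − δ/√(2/35)) + Φ(−1.96 − δ/√(2/35)), with √(2/35) = 0.239.

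| f | s | δ | Rejection probability (nominal 5%) |
|---|---|---|---|
| 5% | 1 | 0.05 | 5.5% |
| 10% | 1 | 0.10 | 7.0% |
| 10% | 2 | 0.20 | 13.3% |
| 20% | 2 | 0.40 | 38.7% |

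**4. No request by four hours.** If such patients leave the analysis and are not replaced, power at 0.68 SD falls from 80.1% to 78.2% with 3 lost from one arm (35 v 32), and to 75.2% with 7 lost (35 v 28). The loss of power is small. The larger issue is that the losses could depend on treatment, with nothing on the forms to show why a patient made no request.

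**The case against.** The case against is substantial, and much of it stands.

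- **Other safety routes exist.** A doctor with at most two patients speaks to each one every 10 minutes. Section 11.0 says of morphine: "The most serious side effect is respiratory depression, particularly with rapid administration". Respiratory rate is counted and does not depend on patient report. The patient scale stops at 3, so a grade 4 toxicity cannot come from it, which implies a separate clinical judgement. A reader might infer that an over-sedated patient would be missed as a safety case; the documents do not support that. What remains is that no sedation item and no source for the grade are specified.
- **The inflation is conditional.** The patient must be too impaired to request medication yet still give a relief score above zero, and must request within four hours. A reader might infer that every sedated patient is credited with longer relief. The zero-relief case and the four-hour rule contradict that, and losing the most sedated patients could work against the combination. A validly scored 30% is also reported relief, so the added area cannot simply be called false.
- **Other data help.** Pain intensity is recorded beside relief, and patients are told to ask at moderate pain, so high intensity without a request would show. It would be wrong to say that nothing collected separates comfort from sedation. Intensity is, however, also patient-rated.
- **The risk may be small.** Section 5.0 ties methadone's "delayed opioid toxicity with side effects such as sedation, confusion and respiratory depression" to chronic administration, and Section 11.0 calls the common effects less frequent at lower doses. Against this, Section 11.0 itself raises potentiation, and Section 14.0 allows for doubling the dosage after a review at 10 cases.

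**Conclusion.** The point holds as a limited design weakness. Patient report is the only specified record of sedation and confusion after dosing, so they may be under-recorded. A sedation-related delay can enlarge B/A within four hours when relief is scored above zero; beyond four hours the patient may drop out of the comparison. Which of these happens depends on statements in Section 9.0 that conflict, and on a scoring rule for patients who are asleep or cannot answer, which the plan does not give.

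The size cannot be estimated. The 19% to 75% range is one patient's ratio under assumed duration, delay and relief. The 5.5% to 38.7% rejection probabilities rest on assumed shares and shifts confined to the combination arm. A reader might conclude that the primary comparison is biased towards synergy. The documents show only that it could be: they give no sedation rate, and the four-hour rule can act in the opposite direction. The stated power is unaffected by this point. The change is worth making because it is cheap and helps in reading both safety and the AUC.

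**What to change.** 1. At every existing check on Forms 1 and 2, including just before each dose, have the blinded bedside doctor record an observer-rated sedation level (for example awake, drowsy, rousable, hard to rouse) and a yes/no for confusion, beside respiratory rate.
2. Report both by arm. Name them as a source for the NCI toxicity grade, and state who assigns it.
3. State how pain relief is scored when a patient is asleep or cannot answer.
4. Reconcile the two statements in Section 9.0 on four hours without a third request, together with Sections 4.2 and 13.0, and say whether those patients' data are analysed.
5. Pre-specify one sensitivity analysis, labelled supportive. Keep all randomised patients with data and recompute areas A and B, giving no relief credit to intervals with observer-rated sedation above drowsy. State beforehand what is done if this leaves area A at zero. It is deliberately severe, since a sedated patient may also be comfortable. It is still preferable to setting sedated patients aside, which would condition on a variable that treatment may affect.

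The cost is two short items per check and one extra analysis. No new staff, visit or procedure is needed, and the added items change no dose or clinical rule.

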## **11.0 TOXICITIES/SIDE EFFECTS**

Methadone has been in widespread use for decades and has been studied extensively. The most frequently observed side effects include sedation, nausea, vomiting, constipation, confusion and hallucinations, which are more pronounced in ambulatory patients and less common at lower doses. Methadone accumulation is not a concern in the current study because of the single dose design. Methadone-related side effects are easily reversed by naloxone.

Morphine is the standard opioid used for post-operative care. Subjects will receive a dose of 2 mg morphine intravenously, immediately when they request the analgesia medication. This dose may be slightly lower or higher than the dose of morphine received via continuous infusion previously. This may result in temporary improvement or worsening of pain control. The most serious side effect is respiratory depression, particularly with rapid administration. Low doses of intravenous morphine have little effect on cardio-vascular stability. High dose morphine may cause sympathetic over activity, dysphoria and convulsions. Nausea, vomiting, constipation, headache, anxiety, pruritus and urinary retention may be seen at lower doses and easily reversed by naloxone.

Given the relatively small amount of opioid used in the study drug (morphine 1 mg plus methadone 1 mg), we do not expect any side effects. However, due to the potential for synergism and, therefore, potentiation of the effect, we will closely monitor the patient for the presence of side effects (see Section 10, Evaluation During Treatment). NCI Common Toxicity Criteria 3.0 will be used to categorize and grade toxicity. Toxicities of grade 2 or less will be treated symptomatically. For patients with grade 3 or 4 toxicities, morphine and methadone will be stopped and an appropriate alternative analgesic regimen will be started.

## 12.0 CRITERIA FOR THERAPEUTIC RESPONSE/OUTCOME ASSESSMENT

Primary endpoint will be the difference between the pain relief offered by a combination of 1 mg morphine with 1 mg methadone intravenously (IV) and 2 mg of IV morphine alone. The outcome measure will be pain relief evaluated as the area under the curve (AUC) (Houde). AUC is the area under the drug level-time curve made by plotting pain relief (0-100%) to the time to the next request for pain medication (see Appendix 6).

Time (t) for each AUC will include:

For area A:

- t0, time of the first request for the analgesia and open administration of 2 mg morphine;
- t2, 3, ..., n, time of assessments 10 minutes apart;
- tn, time of the second request for the analgesia and study drug administration.

For area B:

- t0, time of the second request for the analgesia and study drug administration;
- t2, 3, ..., n, time of assessments 10 minutes apart;
- tn, time of the third request for the analgesia and completion of the study.

Effectiveness of the study drug will be estimated by comparing it to the open label 2 mg morphine IV. Ratio of pain relief offered by a combination of 1 mg morphine and 1 mg methadone IV to the analgesia provided by open label 2 mg morphine IV will be compared to the ratio of pain relief offered by 2mg morphine given in the blind fashion to the open label 2 mg morphine IV (see Appendix 6).

Hypothesis: AUC B2/A ratio is higher than the AUC B1/A ratio.

### 13.0 CRITERIA FOR REMOVAL FROM STUDY

- Patients that develop complications after surgery resulting in: inability to use the PCA, inability to evaluate the patient or new pain beyond the post-surgical pain.
- Patients who require immediate post-operative opioid analgesia other than PCA morphine.
- Patients who require no analgesic medication 2 hours following the PCA being stopped.
- Patients who require no analgesic medication 4 hours following open label morphine 2 mg IV administration.
- Patients who require no analgesic medication 4 hours following the study drug (1 mg of methadone IV plus 1 mg of morphine IV or 2 mg of morphine IV).
- Patients that require new analgesic medications or analgesic adjuvants (including steroids) for the treatment of pain.

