## 4.2 Intervention

All patients will receive Patient Controlled Analgesia (PCA) with IV morphine as per routine post-operative analgesic care. The total amount of morphine available to patients will be equivalent to the standard amounts used after surgery. Informed consent will be obtained from all patients pre-operatively. The PCA settings will start in the recovery room at 1 mg/hour continuous infusion and 1mg every 10 minutes as needed, clinician activated boluses will be available, and the PCA will be titrated to pain control as needed.

The day after the surgery, the PCA will be stopped temporarily, and we will ask the patient to request pain medication as soon as he feels at least moderate pain (See Appendix 1). If two hours pass before a first request for pain medication is made, the patient will be removed from the protocol. During the period of the trial the doctor will have no other clinical or other responsibilities. A doctor will be available to monitor the time to the patients' request for pain medications, assess pain intensity and administer the drugs to replace the PCA promptly upon the patient's request. No more than 2 patients per doctor per floor will be enrolled on the same day.

Upon the first request for analgesia, immediately before administration of morphine 2 mg and every 10 minutes after administration of morphine 2 mg, we will record the patient's pain relief, pain intensity, respiratory rate, and side effects as reported by the patient. If four hours pass before a second request for pain medication is made, the patient will be removed from the protocol.

Upon the second request for analgesia, immediately before administration of the blinded study drug (1 mg of IV methadone plus 1 mg of morphine or 2 mg of IV morphine), every 10 minutes thereafter, and at the time of the third request for analgesia, we will record the patient's pain relief, pain intensity, respiratory rate, and side effects as reported by the patient.

Upon a third request for analgesia, the study is completed and the PCA will be restarted at the pre-study dose. If four hours pass before a third request for pain medication is made, the patient will be removed from the protocol.

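### Patients with no third request within 4 hours of the blinded drug are called both completed and removed, so the end of area B and their place in the primary B/A comparison are contradictory

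*Combined protocol and SAP*

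**What the plan says.** The primary outcome is the ratio of two areas under the pain-relief curve: area B after the blinded drug, divided by area A after open-label morphine.

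- **End of area B.** Section 12.0 ends it at the "time of the third request for the analgesia and completion of the study". Section 14.0 has the same end point: "time of the third request for analgesic medication and completion of the study".
- **Removal.** Section 4.2: "If four hours pass before a third request for pain medication is made, the patient will be removed from the protocol". Section 9.0, item 3, repeats that rule. Section 13.0 lists "Patients who require no analgesic medication 4 hours following the study drug" among its removal criteria.
- **Completion.** The same item of Section 9.0 begins: "Upon a third request for analgesia medication or after four hours if no medication is requested, the study is completed".
- **Projection.** If relief at the second administration is above baseline, Section 14.0 says "projected AUC will be used, extending it to the baseline". The second administration is where area A ends. No corresponding rule for the end of area B is visible.
- **Sample size.** Sections 1.0 and 14.0 count 35 patients per arm who complete the study.
- **Data.** Assessment Form 2 (Appendix 5) schedules relief scores every 10 minutes up to 240 minutes after the study drug.

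The Appendix 6 schema, to which Sections 12.0 and 14.0 refer for the AUC, is not visible in the copy reviewed. A stretch of text directly after the Section 14.0 text is also missing. What follows concerns the visible text only.

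**The concern.** A patient who needs nothing more for four hours after the blinded drug is among the longest responders. On one sentence of Section 9.0 that patient has completed, area B can close at four hours, and the patient counts towards the 35. On the next sentence the patient is removed, and no visible text says whether the area is still analysed. Two analysts could both follow the plan and compute the primary outcome on different patients.

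This four-hour rule differs from the earlier removals. The one for "Patients who require no analgesic medication 4 hours following open label morphine 2 mg IV administration" acts before the blinded drug is given, so it cannot depend on the randomised treatment. The rule after the study drug can. If it is applied as exclusion and the combination prolongs relief, the combination arm loses more patients, and the comparison is no longer between the groups that were randomised.

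**Working it through.** **The plan's own figure.** Section 14.0 states 80% power for a difference of 0.68 SD in mean B/A, 35 per arm, two-sided 0.05. The noncentral t calculation gives 80.1%. The figure reproduces and is not in dispute. It applies to completers, so the status at four hours decides who counts.

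**The passages side by side, for a patient with no third request by 240 minutes.**

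| Place | Status | Area B |
|---|---|---|
| 4.2, 13.0 | removed | not stated |
| 9.0 item 3, first sentence | completed | could close at 240 min |
| 9.0 item 3, next sentence | removed | not stated |
| 12.0, 14.0 | not stated | ends at third request and completion |

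**How many patients could be affected.** The documents give no rate of non-request, so every input here is assumed: lognormal request times with log-SD 0.7, and a median on the combination twice that on morphine. Then

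P(no request by 240 min) = 1 − Φ( ln(240/median) / 0.7 ).

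| Morphine median | Morphine | Combination (doubled median) |
|---|---|---|
| 30 min | ln(8)/0.7 = 2.97, 0.15% | ln(4)/0.7 = 1.98, 2.4% |
| 60 min | 1.98, 2.4% | ln(2)/0.7 = 0.99, 16% |
| 90 min | 1.40, 8% | 0.41, 34% |
| 120 min | 0.99, 16% | 0, 50% |

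Patients with no second request by 240 minutes are already out. If a patient's two request times are correlated, this lowers the rates slightly; at correlation 0.7 the 60-minute row becomes about 1.6% and 14%. Over medians of 60 to 120 minutes and correlations of 0 to 0.7 the ranges are about 2-16% on morphine and 14-50% on the combination.

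**What removal and a cap each do to the mean B/A difference.** Further assumptions: the ratio is (relief in B × time in B) / (relief in A × time in A), with mean relief in each period drawn independently from a beta(4,5) distribution. The table shows shrinkage of the difference relative to an area B followed without limit, for a doubled median. Each cell gives cap at 240 minutes / removal.

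| Correlation | 60 min | 90 min | 120 min |
|---|---|---|---|
| 0 | 24% / 46% | 44% / 65% | 60% / 77% |
| 0.3 | 18% / 31% | 36% / 49% | 50% / 60% |
| 0.5 | 14% / 22% | 30% / 37% | 43% / 47% |
| 0.7 | 11% / 13% | 24% / 23% | 35% / 32% |
| 0.85 | 9% / 7% | 19% / 13% | 29% / 18% |

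The premise in Section 14.0 that "each patient will serve as his own control" makes the positive correlations the more relevant rows. With no treatment difference, removal is equal in the two arms and the mean B/A difference stays within 0.01 of zero.

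**The case against.** The strongest defence is that the plan does supply an end point. Area B ends at the third request and completion of the study, and Section 9.0 says completion occurs at four hours if nothing is requested. Together these give 240 minutes, and Form 2 collects scores to that time. This stands in part. A reader might infer that area B has no end point at all, and the documents do not support that: a 240-minute end can be derived. But the next sentence of Section 9.0, and Sections 4.2 and 13.0, contradict it by removing the same patient.

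A reader might also infer that the plan excludes these patients from analysis. It does not say so. Removal is from the protocol or study, and no visible text defines the analysis population. Exclusion is a permitted reading, and the removal rates above matter for the analysis only under it. The unseen Appendix 6 schema and the missing text could settle the point.

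It is also fair to say that the effect may be negligible if request times are short, and that a 240-minute cap does not always preserve more of the difference than removal does. The table shows the advantage vanishing or reversing at correlations of 0.7 or more with medians of 90 minutes or longer, and at 0.85 with a 60-minute median. That comparison cannot justify the fix.

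**Conclusion.** The contradiction is real, lies in adjacent sentences, and bears on the primary outcome and on who counts towards 35 per arm. It should be resolved before unblinding. Confidence is medium, because part of the material is not visible and exclusion is not a stated rule.

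The size cannot be fixed from the documents. Under the assumed request times, exclusion would remove about 2-16% on morphine and 14-50% on the combination for morphine medians of 60 to 120 minutes, and about 0.1% and 2% at 30 minutes. A reader might infer that the plan could produce a false positive. The illustration does not support this: with no treatment difference, removal is balanced and no bias is expected. The issue is an ambiguous analysis set and, if the combination works, a comparison that no longer preserves randomisation.

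**What to change.** - In Sections 12.0 and 14.0, end area B at the third request or 240 minutes after the study drug, whichever comes first, using the Form 2 scores. Include patients who reach 240 minutes without a request in the primary B/A analysis and among the 35 per arm.
- Apply one projection rule to both areas. Either compute A and B only from observed scores up to the next request or 240 minutes, or state how the Section 14.0 projection to baseline applies to each. Otherwise an unprojected B may be divided by a projected A.
- Report by arm how many reach 240 minutes, and give a completers-only analysis as a sensitivity check.
- Reconcile Sections 4.2, 9.0 and 13.0 on completion versus removal. Clinical handling at four hours is for the investigators; the analysis rule does not depend on it.

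The cost is wording in five sections, with no new visits or data. The plan should state the downside: the cap shortens area B for the longest responders and can itself shrink the measured difference, by about 11-60% against an uncapped area in the 60 to 120 minute illustration at correlations of 0 to 0.7. The reason to keep these patients is to preserve the randomised comparison.
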